Defining PK of OXT in plasma after peripheral administration is required in order to determine PK / pharmacodynamic (PK/PD) relationships for actions centrally, the primary focus for much of neuroscience OXT research, and peripherally, the focus of our primary hypothesis regarding analgesic and disease-modifying effects of OXT in pain after injury. This requires measuring OXT with a reliable, sensitive, and specific assay to define PK and using the knowledge of PK to design dosing schemes with reliable measures of drug action at sites of interest. It also requires creation of outcome measures in the periphery (beyond those peculiar to obstetrics) and centrally which can be repeatedly measured at frequent intervals adequate for PK/PD modeling. These are the goals of this clinical project within a multi-project NIH proposal (P01-NS119159).

i.n. administration is far more practical for subacute and chronic treatment, as would be needed in clinical trials, and the purpose of the current study is to determine the bioavailability and PK of OXT after i.n. administration. The proposed study utilizes a multi-visit, crossover design. In order to determine bioavailability, each subject will receive OXT by intravenous injection on one occasion and i.n. on others. To determine linearity of OXT bioavailability across doses to be subsequently studied, two i.n. OXT doses will be administered on different occasions. Subjects will be stratified across three age groups from young adults to the elderly, with balanced recruitment by sex in order to assess covariates of age and sex in OXT PK.

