## Methods and Measures

Equal numbers of adult men and women will be recruited. Sample size will be divided into 3 groups; young (18-39-year-old) middle (40 – 59-year-old) and older (60 – 75-year-old).

Subjects will report to the CTSI Clinical Research Unit (CRU) for two visits, separated by at least 5 days. On study visit one informed consent will be obtained and eligibility verified. Then two intravenous (IV) catheters will be inserted, one in each forearm, with one for drug infusion and the other for blood sampling. After baseline measures, subjects will receive oxytocin (Pitocin®), 14  $\mu$ g (8.2 IU) over 30 minutes. This dose and infusion duration were chosen based on previous studies showing no adverse events in 10 volunteers and our preliminary PK model which predicts that plasma oxytocin concentrations will be above the limit of detection (1 pg/ml) at 120 min. Venous blood samples (5 ml) will be obtained at 2, 5, 10, 20, 30, 40, 50, 65, 90, and 120 minutes after the initiation of oxytocin administration for oxytocin assay.

On study visit 2, one IV catheter will be placed for blood sampling. After baseline measures, subjects will receive 102  $\mu$ g (60 IU) intranasal oxytocin (Tonix-1900, Tonix Pharmaceuticals, Chatham, NJ). Venous blood samples (5 ml) will be obtained at 1, 2, 5, 7, 10, 15, 20, 25, 35, 45, and 60 minutes after the initiation of the oxytocin administration for oxytocin assay. See graph 3 for rationale for the times of sampling.

**Figure 2. A)** PK modeled OXT concentrations in preliminary data compared with published reports. **B)** Fraction of targeted concentration using TCI. 95% prediction intervals from LC/MS or ELISA assays of duplicate samples (n=11).

We will abandon an individual participant's study and schedule another participant should we be unable to successfully place the intravenous catheters.

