## **STUDY DESIGN**

This is a sequential study of subjects, all of whom will receive, on different occasions, an intravenous infusion or intranasal (i.n.) sprays of oxytocin. Blood samples will be obtained thereafter in order to create a mathematical model to describe the concentrations of oxytocin in the blood over time (pharmacokinetics). In this study, healthy volunteers are recruited for two study drug visits. They will come to the CRU and have two IV catheters inserted, one in each arm for the first study visit. They will receive a 30 minute infusion through one of the IV catheters of oxytocin, 14  $\mu$ g, and blood will be obtained at several times over the next 120 minutes and the amount of oxytocin measured in the blood samples. They will come a second time to the CRU and have one IV inserted in their arm and self-administer i.n. oxytocin, 102 ug over 5 min and blood will be obtained several times over the next 60 minutes and the amount of oxytocin measured in the blood samples. Plasma oxytocin concentrations and individual subject characteristics (age, sex, weight, height, race, and ethnicity) will be analyzed by another group at Stanford University funded under the same NIH grant supporting the work at Wake Forest. The effect of these subject characteristics on the pharmacokinetics of oxytocin will be examined, since these characteristics alter concentration over time of some drugs. Should these characteristics alter oxytocin concentrations, we and others could adjust the dose of oxytocin to the individual.

The main purpose of this study is to sample blood and calculate the pharmacokinetics of oxytocin. We will also assess adverse events during the study.

The research participants will not benefit from this study, but the knowledge we get will be important not only to adjust oxytocin dose to individuals, but to study its possible effects on pain in a more precise way by controlling the amount of oxytocin in the blood circulation. The sample size we chose is needed to get an accurate estimate for the parameters in the pharmacokinetic model for the population in general, not just the subjects in this study.

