## **Interventions and Interactions**

**Study Visit 1:** The participant will report to the Clinical Research Unit (CRU) of the Wake Forest Clinical Translational Science Institute (CTSI), in the morning after having had nothing to eat or drink since midnight. The participant will review and sign the Informed Consent. After informed consent is adequately obtained, a detailed medical history will be obtained from the participant, female participants will have a urine pregnancy test performed to determine pregnancy status. Vital signs to include blood pressure (BP), heart rate (HR), respiratory rate (Resp) and peripheral oxygen saturation (POX) will be measured and recorded along with height and weight.

Once eligibility has been determined; baseline vital signs (BP, HR, Resp, POX) will be obtained for a baseline measurement and then at the following intervals after the infusion has been initiated; 5, 10, 30, 60, 90 and 120 minutes. Two intravenous catheters will be inserted, one in each arm, and baseline measurements will be obtained. Then 14 µg (8.2 IU) oxytocin (Pitocin®), obtained from the research pharmacy, will be infused over 30 min through one of the catheters. Blood (5 ml) will be sampled from the other catheter at 2, 5, 10, 20, 30, 40, 50, 65, 90, and 120 minutes after the initiation of oxytocin, placed on ice, plasma separated in a refrigerated centrifuge, and stored at -80°C until analyzed for oxytocin concentration. The study will not be blinded. The intravenous catheters will be removed after all data collection and the subject discharged from the CRU. The duration for study visit 2 will be approximately 3.5 hours.

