meaningfully contribute to accuracy in future patients. We will study 24 subjects. Bootstrap analysis indicates that the confidence interval for studies of 20 individuals using the LC/MS assay will determine the PK parameters with a corrected confidence range < 20%. A corrected confidence range less 20% implies that mixed effect analysis will distinguish covariate effects in the range of 40% in a study with 20 or more subjects. This is the range at which the covariate effect may be clinically consequential. In practice, mixed-effects analysis with NONMEM is often sensitive to covariate effects smaller than predicted by preliminary analyses. The sample size is increased to 24 to provide stratification by age (3 strata), weight (2 strata), and sex. The crossover design permits accurate determination of i.n. bioavailability and dose linearity despite expected high inter-subject variability in absorption.

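### The plan claims to determine intranasal dose linearity, but every subject gets the same single intranasal dose, so linearity cannot be estimated

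*Combined protocol and SAP*

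**What the plan says.** Two places describe a study that examines dose linearity. The Background, Rationale and Context section gives the aim, "To determine linearity of OXT bioavailability across doses to be subsequently studied", and the means: "two i.n. OXT doses will be administered on different occasions". It also says that "each subject will receive OXT by intravenous injection on one occasion and i.n. on others"; the plural implies at least two intranasal occasions, hence at least three dosing visits. The Analytical Plan then credits the design with the result: "The crossover design permits accurate determination of i.n. bioavailability and dose linearity despite expected high inter-subject variability in absorption".

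The operational sections describe a smaller study. Methods and Measures: "Subjects will report to the CTSI Clinical Research Unit (CRU) for two visits, separated by at least 5 days". Study Design: "In this study, healthy volunteers are recruited for two study drug visits". At visit 1, under Interventions and Interactions, 14 µg of oxytocin "will be infused over 30 min through one of the catheters". At visit 2 subjects "self-administer i.n. oxytocin, 102 ug over 5 min". The Study Visit 2 section gives the same 102 µg, as one spray per nostril repeated after 5 minutes. The primary outcome names only the 102 µg intranasal dose, and the payment schedule covers only these two visits.

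**The concern.** Linearity of bioavailability is a statement about how the absorbed fraction changes, or does not change, as the dose changes. Testing it needs at least two intranasal dose levels. The schedule has one, identical for every subject, so the Analytical Plan attributes to the design a property that it lacks.

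The Background ties the linearity assessment to the doses of later studies and presents the intranasal route as the practical one for longer treatment. Someone planning such a study from the Background and the Analytical Plan could apply the bioavailability found at 102 µg to another dose, believing proportionality had been tested. If the absorbed fraction depends on dose, for example through saturable absorption or run-off of spray, the planned analysis would give no warning. The document also contradicts itself on how many doses and occasions each subject receives.

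**Working it through.** The plan gives no precision or power figure for linearity, so there is none to reproduce. The check is a count followed by an identifiability argument.

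**Step 1. Count.**

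| Item | Background | Operational sections |
|---|---|---|
| Intranasal dose levels | 2 | 1 (102 µg) |
| Dosing visits | at least 3 (1 intravenous, 2 or more intranasal) | 2 |

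The operational column is the same in Methods and Measures, Study Design, the two visit descriptions, the primary outcome and Volunteer Payment. No linearity analysis appears in the objectives, the outcomes or the modelling steps.

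**Step 2. Identifiability.** Take the simplest model that allows bioavailability to vary with dose. Let I = 1 for intranasal and 0 for intravenous dosing, and D the dose in µg:

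log(AUC/D) = a + I·f + I·β·log(D)

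The intravenous visit fixes a (clearance), f sets the level of log bioavailability, and β is its slope on log dose. Linearity means β = 0. The distinct design rows, in the order (a, f, β), are:

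- intravenous 14 µg: (1, 0, 0)
- intranasal 102 µg: (1, 1, log 102) = (1, 1, 4.62)

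The third column is 4.62 times the second, so the rank is 2 for 3 parameters. Only f + 4.62β can be estimated; f and β cannot be separated. More subjects repeat the same two rows, so neither 24 nor 30 subjects changes this.

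**Step 3. Could anything else supply a second level?**

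- *14 µg intravenous against 102 µg intranasal.* Dose is completely confounded with route, so any dose effect is absorbed into bioavailability.
- *The two spray pairs.* They are parts of one 102 µg dose. Of the 11 samples (1, 2, 5, 7, 10, 15, 20, 25, 35, 45 and 60 min), only those at 1, 2 and 5 min fall before or at the second pair. They do not give total exposure after half the dose.
- *The preliminary data.* The 11 earlier subjects received intravenous oxytocin, so pooling adds no intranasal level.
- *Variation between subjects.* None is planned.

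**Step 4. What a second level would do.** Adding an intranasal row at 51 µg (an assumed example, half of 102) gives (1, 1, log 51) and rank 3 of 3, so β becomes estimable. For its precision with 24 subjects, let s = √log(1 + CV²), where CV is the within-subject coefficient of variation of intranasal AUC, and let r be the dose ratio:

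- SE(β) = s·√(2/24) / log r
- 90% CI half-width = 1.714·SE(β) (t distribution, 23 degrees of freedom)

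The documents give neither a second dose nor this CV, so both are assumptions:

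| CV | half-width, r = 2 | half-width, r = 4 |
|---|---|---|
| 30% | ±0.21 | ±0.11 |
| 50% | ±0.34 | ±0.17 |
| 70% | ±0.45 | ±0.23 |

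For example, at CV 50% and r = 2: s = √log 1.25 = 0.472; SE = 0.472 × 0.289 / 0.693 = 0.197; half-width = 1.714 × 0.197 = 0.34. Even with a second dose, then, whether linearity is determined accurately would depend on the dose ratio and the within-subject variability.

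**The case against.** The best defence is that little depends on the claim. Linearity is absent from the main objective, the additional objective, the primary outcome, the modelling steps and the sample size argument. In the Analytical Plan it is two words in a closing sentence. Deleting them changes no dose, visit, sample, test or sample size. The operational sections agree on dosing, so staff know what to give. No linearity estimate can be produced from these data, so no false one can be reported, and anyone who reads the visit schedule will see the single level. The harm to later studies is indirect, since those studies are not described here.

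There is also a technical point. Capacity-limited absorption can alter the shape of a concentration curve after a single dose, so 11 samples over 60 minutes are not wholly uninformative about saturation.

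Much of this stands. The defect is confined to the linearity claim and the design description that goes with it, and within-subject estimation of bioavailability at 102 µg is sound on this point. The technical point also stands in a narrow sense, but such inference would be weak, would depend on the assumed model and is not planned. It does not amount to accurate determination of linearity. Nor is the mismatch merely clerical: the Analytical Plan asserts a capability that the design cannot have, and the Background links it to future dosing.

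**Conclusion.** The concern holds. The schedule has one intranasal dose level where the Background states two, and two dosing visits where the Background implies at least three. The slope of bioavailability on dose therefore has zero degrees of freedom at any sample size. This conclusion needs no assumption about variability; it requires only that the operational sections, which agree with one another, describe the study to be run. Absorption rate and bioavailability remain targets that can be estimated at 102 µg. What must go is the claim that the study says anything about other doses.

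**What to change.** Bring the Background and the Analytical Plan into line with the visit schedule:

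- In the Analytical Plan, delete dose linearity from the sentence on what the crossover design permits.
- In the Background, delete the sentence giving two intranasal doses as a test of linearity, and change the plural intranasal occasions to one.
- Add a statement that bioavailability and absorption rate are estimated at 102 µg only, that linearity is not assessed, and that use of the estimate at other doses is an untested assumption.

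The cost is wording only; the study gives up a claim that it cannot support.

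If the sponsor does want linearity, wording will not be enough. The protocol would need a second intranasal dose level at its own visit, with a sampling schedule, an outcome, a prespecified linearity analysis and a precision calculation based on the chosen dose ratio and a justified within-subject CV. That adds at least one visit per subject, with the corresponding assays and payment.

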## **Human Subjects Protection**

### **Subject Recruitment Methods**

Healthy subjects will be recruited from our current database of volunteers BG05-468, word of mouth and Be Involved website; The research nurses; [name] and [name], LPN will conduct the recruitment of study subjects.

Potential subjects from the database will be contacted via phone or email, per their request. Potential subjects from the Be Involved website will be contacted according to the information they provide.

### **Informed Consent**

Signed informed consent will be obtained from each subject. [name] or [name], LPN will obtain consent. Potential subjects will be consented in the CRU. A private room will be utilized during the consent process and all study visits.

### **Confidentiality and Privacy**

Confidentiality will be protected by collecting only information needed to assess study outcomes, minimizing to the fullest extent possible the collection of any information that could directly identify subjects, and maintaining all study information in a secure manner. To help ensure subject privacy and confidentiality, only a unique study identifier will appear on the data collection form. Any collected patient identifying information corresponding to the unique study identifier will be maintained on a linkage file, stored separately from the data. The linkage file will be kept secure, with access limited to designated study personnel. Following data collection subject identifying information will be destroyed 3 years after closure of the study, in confidential shredding disposal bins consistent with data validation and study design, producing an anonymous analytical data set. Data access will be limited to study staff. Data and records will be kept locked and secured, with any computer data password protected. No reference to any individual participant will appear in reports, presentations, or publications that may arise from the study.

### **Data Sharing Plan**

Plan Description: Statistical programs in the data analysis will be written in R. The software and anonymized data will be included both as digital supplements in the published papers and will be posted on GitHub under [github.com/[name]](https://github.com/[name]). Interested investigators will be able to reproduce the published analyses from these files. Consistent with the posting of software and data to the OpenTCI initiative, the software and de-identified data will be made available with "no strings attached," enabling investigators to freely use the data to inform or supplement additional research without restriction. Data to be made available are oxytocin dose, times of sampling (relative to the start of dosing), plasma oxytocin concentrations at those times for each subject, and age, weight, and sex for each subject.

### **Data and Safety Monitoring**

The principal investigator will be responsible for the overall monitoring of the data and safety of study participants. A Data Safety Monitoring Committee will include [name]., Associate Professor, Section Head Obstetric and Gynecologic Anesthesia and [name]., Associate Professor, Anesthesiology. A cumulative report will be sent to the committee to review quarterly and all serious and unexpected adverse events will be reported to the committee for review and recommendations.

### Volunteer Payment

Participants will be paid a total of \$500 according to the following payment schedule which we have used throughout the last 2 cycles of this grant's protocols. We believe that this payment schedule is fair and appropriate, paying for each procedure attempted and an additional payment for completion of the entire study.

Study Visit 1: 2 PIV \$25/each (\$50); \$100 for PK sampling

Study Visit 2: 1 PIV \$25; \$100 for PK sampling + \$225 for completion of study visit 2 PK sampling

Subject must complete all of the above phases to receive this payment.

If 2 PIV's cannot be placed on Visit 1: subject will be compensated \$50 and subject replaced

### Long-term Follow-up

Volunteers will be contacted daily for one week and questioned about adverse events from the study.

### Reporting of Unanticipated Problems, Adverse Events or Deviations

Any unanticipated problems, serious and unexpected adverse events, deviations or protocol changes will be promptly reported by the principal investigator or designated member of the research team to the IRB, DSMC and FDA as required by each.

